### **Specific Aim 3: Dyspnea on Exertion in Obese Children**

Introduction: DOE During Constant Load Submaximal Exercise. The *working hypothesis* is that childhood obesity will increase DOE and alter respiratory function during constant load submaximal cycling, but to a greater extent in obese children with respiratory symptoms misdiagnosed as asthma. The *rationale* behind the proposed research centers on the fact that exercising will force EELV to even lower levels in obese children creating the potential for significant breathing limitations. If low enough, obese children could experience tidal expiratory flow limitation, constrained expiratory tidal volume expansion, and decreased ventilatory capacity. It is unclear whether these respiratory effects or changes in body composition will be linked with DOE in obese children (i.e., increased RPB as it is in obese adults). Furthermore, we propose that obese children with respiratory symptoms misdiagnosed as asthma will have greater changes in EELV or differences in peripheral airways function making them more susceptible to the limitations of low lung volume breathing and/or increased ratings of dyspnea on exertion.

Methodology, experimental protocol, and measurements. The strategy will be to determine respiratory function, breathing mechanics, and DOE during 6 minutes of constant load submaximal exercise cycling at 30W (8-9 yr olds) or 40W (10-12 yr olds) and during 6 minutes of constant load cycling at 50% of peak  $\dot{V}O_2$ . We will measure HR, BP, SpO2%, PETCO2, gas

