### **Statistical Considerations**

Co-investigator [name] (UT Southwestern Division of Biostatistics) is the statistical co-investigator on this project and has assisted in the development of the statistical plan; she will also

Total n=96	Obese	Obese misdiagnosed with asthma	Non- obese
Boys	n=24	n=12	n=12
Girls	n=24	n=12	n=12

direct the data analysis on an on-going basis.

Statistical Plan. Our plan is to complete testing in nonobese and two obese groups, boys and girls separately but concurrently. Thus, sample size calculations are based upon within-gender comparisons per allocation in table at right. In Aims 1-3, comparisons will be made between nonobese, obese, and obese children misdiagnosed with asthma within the same gender with analysis of variance models (ANOVA). Pairwise group comparisons will be made using least squares means contrasts derived from the linear models. Data transformations or nonparametric tests will be utilized as needed to meet analysis assumptions. At baseline, ISSAC and ECRHS asthma screening questionnaire scores will be compared among groups with the Kruskal-Wallis test. Comparisons for Aim 4 will be made similarly, but with the addition of repeated measurements to assess the two obese groups and the nonobese children of the same gender at baseline and at 1 year of follow-up. Additional assessments of gender effects will be performed as part of a secondary analysis, but we are not powering the study to detect interaction by gender. Alpha is set at 0.05 for ANOVA and planned contrast power (PASS 11, NCSS, LLC, Kaysville, UT), described below . Data will be analyzed using SAS version 9.4 (SAS Institute, Inc., Cary, NC).

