Aim 1. Our primary variable is FRC measured while seated upright (Aim 1a) and when lying supine (Aim 1b). Based upon our preliminary data for seated FRC (%TLC) in nonobese boys (mean± SD, 42.4±2.5) and obese boys (36.5±6.2), it is calculated that a mean difference in FRC (%TLC) of 5.1 can be detected with statistical power of 81%, alpha=0.05, pooled SD of 5.0, comparing 24 obese to 12 nonobese children or to 12 obese children misdiagnosed with asthma. Our data also show that the differences may be larger for girls than boys, so power for a test between obese girls and obese girls misdiagnosed with asthma will be at least 80%. Similarly, for children lying supine, nonobese boys have an FRC (%TLC) of 34.4±8.8 vs. 23.1±3.4 obese, a more conservative difference of 6.0 %TLC is detectable with 80% power. In our formal protocol, we anticipate being able to make precise and reproducible measurements, and have confidence that we can meet our goals with the sample size proposed. Preliminary data demonstrate that these measures and effect sizes are feasible.

Aim 2. Our primary variable is peak  $\dot{V}O_2$ . From our preliminary peak  $\dot{V}O_2$  (ml/min/kg) for nonobese (41.9±4.9) and obese boys (26.3±3.9), it is calculated that our study will yield power of 80% to detect a clinically relevant mean difference of 4.7 ml/min/kg for obese versus nonobese children or obese children misdiagnosed with asthma, anticipating smaller differences than the 16 ml/min/kg mean difference observed from our data in obese versus nonobese. Effect size estimates for girls are anticipated to be similar.

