Aim 3. Our primary variable for Aim 3 is RPB during constant load exercise. Preliminary data from children in our lab show that RPB at constant load is very similar between nonobese and obese children of both genders (e.g., girls, 3.4±0.6 vs. 3.3±1.5), which would not be detectable with a reasonable sample size. This is in contrast with our previous studies of RPB in nonobese (2.1±1.3)  and obese women with DOE (4.7±1.2) , where only 6 subjects would have been necessary per group to detect significant differences. At this time our preliminary sample of children is small, and we anticipate that future experience could be more like that in the adults, but we need to carry out the designed studies at a feasible sample size (96 total including nonobese controls) to find out. These effects contrast with another important variable for Aim 3; the EELV during constant load exercise. Based upon EELV (%TLC) data from obese girls (28±3) during exercise, we would be able to detect differences of 3.2%TLC between the 3 groups at greater than 80% power (also note how low the EELV is in the obese children during exercise). We expect similar differences and power in studies with boys.

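### Aim 3: the claim of more than 80% power at 3.2 %TLC in EELV holds for the two 24 v 12 contrasts but, at the printed SD of 3, not for nonobese v misdiagnosed (12 v 12)

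*Combined protocol and SAP*

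**What the plan says.** The Statistical Plan under Statistical Considerations says that "sample size calculations are based upon within-gender comparisons per allocation in table at right". For each gender the table gives 24 obese, 12 obese misdiagnosed with asthma and 12 nonobese children. For Aims 1-3 the groups are compared by ANOVA, and "Pairwise group comparisons will be made using least squares means contrasts derived from the linear models". Alpha is 0.05 for both the ANOVA and the planned contrasts.

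The primary variable of Aim 3 is the rating of perceived breathlessness (RPB). The plan concedes that the RPB difference in its preliminary data on children would not be detectable with a reasonable sample. It then turns to "another important variable for Aim 3; the EELV during constant load exercise". The power statement for that variable opens "Based upon EELV (%TLC) data from obese girls (28±3) during exercise" and concludes "we would be able to detect differences of 3.2%TLC between the 3 groups at greater than 80% power". Similar differences and power are expected in boys.

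**The concern.** Three groups give three pairwise contrasts, and these are not the same size. Two compare 24 children with 12 (obese v nonobese, obese v misdiagnosed). The third, nonobese v misdiagnosed, compares 12 with 12. One power figure at one difference cannot describe both kinds, yet the Aim 3 sentence covers all three groups without exception. The Aim 1 paragraph is more careful: it names the two 24 v 12 comparisons to which its figure applies.

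At stake is how a null EELV result for nonobese v misdiagnosed would be read. A reader would credit it to a test with more than 80% power at 3.2 %TLC. At the printed SD the chance of missing a true difference of that size is nearer 28-30%.

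**Working it through.** **Inputs**
- Group sizes per gender: 24 obese, 12 misdiagnosed, 12 nonobese (table in Statistical Considerations).
- Difference 3.2 %TLC and SD 3 (Aim 3 paragraph). This is the only EELV SD printed for children, so it is taken for all groups.
- Alpha 0.05 (Statistical Plan). Sidedness is not stated; two-sided is inferred. The Aim 1a figure of 81% (difference 5.1, SD 5.0, 24 v 12) reproduces as 80.0-80.6% two-sided, but would be 88% one-sided.

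**Formula.** The noncentrality is λ = d / (SD × √(1/n₁ + 1/n₂)). Power = P(|T| > t₀.₉₇₅,df), where T is noncentral t with parameter λ. Two error terms are shown: a two-sample t-test with df = n₁ + n₂ − 2, and a contrast from the three-group ANOVA with df = 48 − 3 = 45. The ANOVA contrast is the planned analysis.

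**Step 1: the plan's own figure, 24 v 12**
- √(1/24 + 1/12) = 0.3536, so λ = 3.2 / (3 × 0.3536) = 3.02.
- Power is 83.4% (df 34) or 83.9% (df 45). The claim of more than 80% reproduces for obese v nonobese and obese v misdiagnosed.

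**Step 2: the remaining contrast, 12 v 12**
- √(1/12 + 1/12) = 0.4082, so λ = 3.2 / (3 × 0.4082) = 2.61.
- Power is 70.5% (df 22) or 72.5% (df 45). A normal approximation, which is optimistic at this size, gives 74.3%. No two-sided version reaches 80%.
- The difference detectable with 80% power is 3.59 %TLC (df 22) or 3.51 %TLC (df 45).

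**Step 3: sensitivity to rounding of the SD.** Values from 2.5 to just under 3.5 all print as 3. Power at 3.2 %TLC (two-sample / ANOVA contrast):

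| SD | 24 v 12 | 12 v 12 |
|---|---|---|
| 2.5 | 94.0% / 94.3% | 85.0% / 86.6% |
| 3.0 | 83.4% / 83.9% | 70.5% / 72.5% |
| 3.49 | 71.2% / 71.8% | 57.4% / 59.4% |

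The largest SD that gives 80% power is 2.67 / 2.74 for 12 v 12 and 3.14 / 3.16 for 24 v 12.

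**Step 4: could the statement refer to the overall F test?** Noncentral F with 2 and 45 df, SD 3, largest gap 3.2:
- obese midway between the other two groups: 61%
- misdiagnosed midway: 76%
- only one 12-child group differs: 79.7%
- the 24-child group differs from both others: 90%

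If adjacent groups are each 3.2 apart, with obese in the middle, power is 99.7%, but the extreme gap is then 6.4. The plan states no pattern of means.

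**The case against.** Four points can be made for the plan.

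*Only the 24 v 12 contrasts were meant.* Those are the pairs named for Aim 1, and the claim is true of them. This may well be the intention, but the Aim 3 sentence does not say so, and the general plan includes all pairwise comparisons.

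*The unrounded SD may be small enough.* This stands as a limit on the finding: an SD between 2.5 and about 2.7 would print as 3 and make the 12 v 12 claim true. A reader might infer that the claim is false whatever the underlying data; the documents do not support that. They show that the printed SD does not deliver it.

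*The overall F test was meant.* This helps only for some patterns of means, and none is given.

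*The gap of interest is probably larger.* Aim 3 expects lower EELV in obese than in nonobese children, and supposes that misdiagnosed children "will have greater changes in EELV or differences in peripheral airways function making them more susceptible". If both hold for EELV, nonobese v misdiagnosed is the widest gap. Power for 12 v 12 at SD 3 is 88-89% at 4.0 %TLC and over 99% at 6.4. This largely stands and keeps the consequence small. It does not make the statement at 3.2 correct, and the hypothesis is worded as EELV or peripheral airways, so a wider EELV gap is not assured.

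**Conclusion.** At the printed inputs the Aim 3 power statement is right for two of the three contrasts and overstated for the third. Nonobese v misdiagnosed has about 70-72% power at 3.2 %TLC, roughly 8 to 10 points short of 80%; the detectable difference is about 3.5-3.6 %TLC. This rests on two-sided alpha 0.05 without multiplicity adjustment, a common SD of exactly 3, and the within-gender allocation.

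The consequence is modest. EELV is not the primary variable of Aim 3, and the affected gap is expected to be the widest. Nothing here shows that the sample size is inadequate.

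A reader might go further and infer that the Aim 1a power figures are also wrong, because the pooled SD of 5.0 is applied to obese v misdiagnosed although the preliminary data shown are for "nonobese boys (mean± SD, 42.4±2.5) and obese boys (36.5±6.2". The documents do not support that. The 81% reproduces from its stated inputs and is already confined to 24 v 12. The planned contrast uses the three-group error term, which properly includes nonobese children. No SD for misdiagnosed children is printed, so power for that pair cannot be shown to fall below 80%. Nor is the statement of at least 80% for girls shown to be false. Writing down the SD assumed for misdiagnosed children would be a documentation improvement, not the correction of an error. On unequal variances, the plan already provides that "Data transformations or nonparametric tests will be utilized as needed to meet analysis assumptions".

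**What to change.** In the Aim 3 paragraph:
- Limit the statement of more than 80% power at 3.2 %TLC to obese v nonobese and obese v misdiagnosed (24 v 12, within gender).
- For nonobese v misdiagnosed (12 v 12), state about 70-72% power at 3.2 %TLC, or equivalently a detectable difference of about 3.5-3.6 %TLC at 80% power.
- Give the EELV SD to one decimal and recompute these figures from it. If it is at most about 2.67 (two-sample test) or 2.74 (ANOVA contrast), the present wording can stand for all three contrasts. If it exceeds about 3.14-3.16, the 24 v 12 statement needs revision too.

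The cost is one reworded sentence and one SD looked up in the preliminary data. Enrolment, allocation and analysis do not change.

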#### **Specific Aim 4: Effects of Weight Loss and Regular Exercise and Weight Gain in Obese Children**

Introduction. The *working hypothesis* is that weight loss (or an equivalent reduction in BMI percentile) and regular exercise will improve respiratory function, exercise tolerance, and DOE in obese children, including obese children misdiagnosed with asthma, while continued weight gain (or increase in BMI percentile) will worsen respiratory function, exercise tolerance, and DOE in obese children, including obese children misdiagnosed with asthma, as compared with normal weight children after 1 yr. The *rationale* behind the proposed research centers on the fact that FRC at rest, EELV during exercise, and peak  $\dot{V}O_2$  in ml/min/kg will be increased in obese children after weight loss and regular exercise but decreased by continued weight gain. The cumulative effect of the weight loss program would thereby reduce the potential for breathing limitations at rest and/or during exercise, increase exercise tolerance, and potentially reduce DOE in obese boys and girls, including those misdiagnosed with asthma, but weight gain would have the reverse effects.

Methodology, experimental protocol and measurements. The strategy will be to repeat the measurements detailed in Aims 1-3 after 1 yr: 1) in 12 obese boys and 12 obese girls after weight loss (or an equivalent reduction in BMI percentile) and regular exercise, 2) in 12 obese boys and 12 obese girls after weight gain (or an increase in BMI percentile), 3) in 12 obese boys and 12 obese girls misdiagnosed with asthma regardless of weight changes or exercise participation, and 4) in 12 normal weight boys and 12 normal weight girls. We will test at 1 yr because parents **prefer** to have testing done during summer vacation months only.

*Weight Loss and Regular Exercise* will be prescribed by attending physicians at the **COACH**

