**Aim 4.** Primary variables for Aim 4 are change in FRC at rest, peak  $\dot{V}O_2$ , RPB, and EELV during constant load exercise from before to after 1 year of follow-up. We are gaining experience with studies in children; current preliminary data from n=7 obese children yield similar mean differences and standard deviations as in adults. Therefore, based upon the change in EELV during constant load exercise in obese men before ( $35 \pm 5$ ) and after ( $39 \pm 3$ ) a loss of 13% of body fat, and the change in RPB during constant load exercise in obese women before ( $4.7 \pm 1.1$ ) and after ( $3.2 \pm 1.6$ ) weight loss, our sample will have sufficient power (.80,  $\alpha=0.05$ ) to detect meaningful paired differences (e.g., 1.5 in RPB) with weight loss and regular exercise. We will retest all children after ~1 yr. We expect less than 10% attrition and repeated data on nearly all children will be available for this Aim. Combining the two obese groups (with and with asthma misdiagnosis), the children will be divided into obese who lost weight, obese who gained weight, and control normal weight children and respiratory changes will be compared between groups with ANOVA as described for Aims 1-3. While these categorized weight changes have clinical appeal, weight change analyzed as a continuous variable may be more powerful and informative. Hence, change at 1 year minus baseline will also be evaluated with Spearman or Pearson correlations to quantify the association between 1-year weight change and the change for respiratory function, exercise tolerance, and DOE variables and, with the 36 obese participants analyzed (by gender), a correlation of 0.45 can be detected with 80% power.

To evaluate gender effects, baseline and follow-up measurements for FRC, peak  $\dot{V}O_2$ , RPB, and EELV will be analyzed in mixed-effects repeated measures models with the study participant included as a random effect. Interactions between gender, study group (obese, obese misdiagnosed with asthma, nonobese), and time can be assessed as fixed effects; weight change effect will be modeled as a covariate. PAQ-C score changes will also be assessed with repeated measures models.

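### Aim 4 lets change be judged by weight or by BMI percentile, but its analysis uses weight change only, with no cut-point, no rule for conflicting cases and no height term in growing children

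*Combined protocol and SAP*

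**What the plan says.** All places are in the combined protocol and SAP.

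- **Specific Aim 4, Introduction.** The hypothesis has two alternatives in each direction. Improvement follows weight loss or an equivalent fall in BMI percentile; on the other side, "continued weight gain (or increase in BMI percentile) will worsen respiratory function, exercise tolerance, and DOE in obese children".
- **Specific Aim 4, Methodology.** The retest groups carry the same alternatives: "in 12 obese boys and 12 obese girls after weight loss (or an equivalent reduction in BMI percentile) and regular exercise", and "in 12 obese boys and 12 obese girls after weight gain (or an increase in BMI percentile"). No minimum change is given, and no rule for a child who moves in opposite directions on the two scales. Expected results repeats the BMI-percentile alternative for loss.
- **Specific Aim 4, description of the COACH program.** The initial target is about 10% of body weight or an equivalent BMI-percentile reduction. Equivalence is illustrated only by an example: 2.5 cm of growth lowers the percentile by about 1.
- **Statistical Considerations, Aim 4.** Here only weight appears. For the split, "the children will be divided into obese who lost weight, obese who gained weight, and control normal weight children". For the correlations, the target is "the association between 1-year weight change and the change for respiratory function, exercise tolerance, and DOE variables". In the mixed model, "weight change effect will be modeled as a covariate". BMI percentile, height and growth are not mentioned.
- **Handling of growth.** Methodology uses the retested nonobese children as controls for age and growth.

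**The concern.** The analysis does not carry out the definition that the hypothesis uses. Participants are 8 to 12 years old, and Anticipated problems expects all of them to gain weight, fat weight and/or fat-free weight over the year. A child can therefore gain kilograms while becoming less obese for height and age. Read literally, Statistical Considerations places that child with those who gained, although the hypothesis may count the same child as improving.

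This exposure serves all four Aim 4 primary variables (change in FRC, peak VO2, RPB and EELV). With no stated cut-point or conflict rule, group membership could also be settled after the data are seen. In addition, kilogram change in a growing child mixes change in fatness with growth, and Methodology itself expects age and growth to affect the outcomes.

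**Working it through.** **1. The plan's own figure.** The Aim 4 text gives 80% power for r = 0.45 with 36 obese children per gender. By Fisher's z, two-sided alpha 0.05 (sidedness assumed): atanh(0.45) = 0.4847; 0.4847 × √33 − 1.96 = 0.824; power = 0.795. The figure reproduces. The issue is what the exposure means, not the arithmetic.

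**2. Can the two scales disagree?** Inputs from Anticipated problems: height 143.3 cm; 103 lb (46.7 kg) at the 95th percentile; 155 lb (70.3 kg) at the upper limit. Growth of 2.5 cm is the COACH example, not a stated annual rate.

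- Weight ratio at constant BMI: (145.8 / 143.3)² = 1.0352.
- Gain with no rise in BMI: 46.7 × 0.0352 = 1.6 kg; 70.3 × 0.0352 = 2.5 kg.

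So they can.

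**3. What is 'equivalent'?** At constant weight, 2.5 cm of growth lowers BMI by 1 − 1/1.0352 = 3.4%. A 10% fall from growth alone needs 143.3/√0.9 − 143.3 = 7.75 cm. The 10% target and the 2.5 cm example do not fix one threshold.

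**4. How many children?** The documents give no distribution of weight change or growth. Assumed: weight change normal, mean 0 to 4 kg, SD 4 to 8 kg; growth mean 2.5 cm, SD 1 cm; baseline 60 kg or uniform on 46.7–70.3 kg. A mean of 0 matches the 50/50 preliminary split in Subject Selection. A hand check at 60 kg and exactly 2.5 cm puts the limit at 60 × 0.0352 = 2.11 kg. With mean 0, P(0 < change < 2.11) is 0.20 at SD 4 and 0.10 at SD 8. Simulation gives the share gaining kilograms while BMI falls by at least the stated amount:

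| BMI fall required | 2.5 cm growth | 5.5 cm growth (assumed) |
|---|---|---|
| any | 10–20% | 21–44% |
| 5% | 0.2–0.4% | 7–14% |
| 10% | almost none | under 0.1% |

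For scale, 10–20% of the 72 obese children is about 7 to 15. These shares are on raw BMI, not BMI percentile, and are illustrative.

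**5. Effect on the continuous analysis.** Under the same assumptions, kilogram change and relative BMI change correlate 0.965–0.995. If the outcome follows relative BMI change with r = 0.45, using kilograms gives r between 0.45 × 0.965 = 0.434 and 0.45 × 0.995 = 0.448. Power is then 0.762–0.790 against 0.795.

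**6. Do the controls deal with growth?** Nonobese children enter the three-group ANOVA, and the mixed model has group and time, so average growth in the outcomes is partly covered. Neither adjusts for differences in growth between obese children who lost and who gained. The correlations in the 36 obese children per gender include no controls.

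**The case against.** The strongest reply is that the groups require an *equivalent* reduction, not any reduction. If 'equivalent' means something like the 10% target, almost no child gains kilograms and also qualifies as a loser. That stands as far as it goes. A reader might infer that every child who gains kilograms while BMI dips meets both definitions; the text does not support that. It also does not say what does qualify, so the missing cut-point remains.

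'Lost weight' might be shorthand for the fuller wording. Even so, no cut-point or conflict rule exists, and the correlations and covariate still name weight change.

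Three stronger readings should be set aside.

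- **Large bias or loss of power.** Spurious association through growth is possible, but its size would rest on assumed correlations of growth with exposure and outcome, for which the documents give no values. Step 5 points to a modest effect on the continuous analysis.
- **A larger overlap on percent of the 95th percentile.** The reference rises with age, but the yearly rise implied by the plan's BMI figures depends on the ages chosen. From 33.2 (if that is age 8) to 34.24 at 10.5 years is only about 1.2% a year. No firm range follows.
- **A conflict over the misdiagnosed group.** Methodology retests "in 12 obese boys and 12 obese girls misdiagnosed with asthma regardless of weight changes or exercise participation", while the Aim 4 analysis pools both obese groups by weight change. The first says who is retested and the second how they are analysed, and the mixed model keeps the groups distinct. These are compatible.

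**Conclusion.** The point holds as a mismatch between hypothesis and analysis that should be fixed. The hypothesis and groups accept weight or BMI percentile; all three analyses use weight alone, without a threshold, a conflict rule or a height term. That follows from the text and needs no assumption. That a child can fall on opposite sides follows from the plan's own example child.

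The number affected is not known. It runs from almost none to about one obese child in five at 2.5 cm growth, and higher if growth is faster, depending mainly on the undefined threshold and on assumed distributions. The lost-versus-gained split is the more exposed analysis. No power gain is claimed for the correction; the reasons for it are correct classification and control of growth.

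**What to change.** 1. Define the Aim 4 exposure once, on a growth-adjusted scale. Change in BMI as a percent of the age- and sex-specific 95th percentile is a natural choice, because Overall Strategy already prefers that scale above the 95th percentile.
2. State before analysis the cut-point and one rule for children who meet both definitions or show no change.
3. Use this exposure in the split, the correlations and the mixed model.
4. Add height change as a covariate in the continuous analysis, since relative BMI alone may not fully remove growth. Report raw weight change adjusted for height change as a sensitivity analysis.
5. If kilograms are kept instead, adjust for height change and remove the BMI-percentile alternatives from Specific Aim 4 (Introduction, Methodology, Expected results and Interpretation).

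**Cost.** SAP wording and a little extra analysis. Height and weight are measured under Aim 1a and repeated at 1 year. One covariate lowers power for r = 0.45 at n = 36 from 0.795 to Φ(0.4847 × √32 − 1.96) = 0.783. The exposure is less readable than kilograms. A zero cut-point can also give uneven groups: at mean weight change 0 and 2.5 cm growth, about 11 to 14 of 36 obese children per gender would show a raw-BMI increase, and fewer would rise on percent of the 95th percentile. That could cost the categorical contrast power, so the cut-point should be chosen with group sizes in view, before outcomes are examined.
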